A Different Approach to Preventing Thrombosis (ADAPT): A Randomized Controlled Trial Comparing Low Molecular Weight Heparin to Acetylsalicylic Acid in Orthopedic Trauma Patients

Study Protocol and Statistical Analysis Plan

NCT02774265

7/26/18

Study Design

ADAPT was a single-center randomized controlled trial that compared safety of low molecular weight heparin (LMWH) versus aspirin with respect to bleeding and wound complications in orthopaedic trauma patients within 90-days of their fracture. Ethics approval was obtained by the University of Maryland Institutional Review Board and informed consent was obtained for all enrolled patients.

Eligibility Criteria

All adult trauma patients (age \geq 18 years) with operative extremity fracture proximal to the carpals/metatarsals or any hip or acetabular fracture requiring VTE prophylaxis were included in the study. We excluded prisoners, pregnant patients, non-English speaking patients, patients with an indication for therapeutic anticoagulation or high dose aspirin (greater than 81mg daily) and patients receiving pre-existing confounding prophylaxis or therapeutic anticoagulation prior to admission or greater than two doses of prophylaxis in our hospital prior to consent. Patients with recent VTE within the last 6 months, impaired creatinine clearance, history of heparin-induced thrombocytopenia or aspirin or non-steroidal anti-inflammatory allergy or another contraindication to receiving one of the study medications were also excluded.

Randomization and masking

Patients were randomly assigned venous thromboembolism prophylaxis by LMWH or aspirin using block randomization (6 per block) with the assistance of the trial's REDCap system by research staff at the study site after enrollment. Surgeons and patients were not masked to the treatment groups.

Intervention and Procedures

Patients allocated to the LMWH group received two 30mg BID doses daily with allowance for dose adjustment based on BMI or Xa levels. Patients allocated to the aspirin group received 81mg doses, twice daily. The duration of prophylaxis was at the treating surgeon's discretion, with no minimum or maximum duration. Mechanical prophylaxis with intermittent pneumatic compression devices is also ordered as part of clinical protocol for all inpatients. Study follow-up was conducted at 3-months post-fracture either at the patient's clinic appointment or over the phone. A chart review was also conducted at this time.

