All prophylaxis doses were monitored daily during the index admission by the study's research staff. Additionally, outpatient adherence was assessed at all clinical follow-up visits. Any contamination or unplanned crossover was closely monitored.

Outcomes

The primary endpoint was bleeding complications within 90-days from the date of injury. Bleeding complications included a 2g/dL or greater drop in hemoglobin, blood transfusion, gastro-intestinal (GI) bleeding, surgical site hematoma requiring reoperation, or other bleeding events requiring intervention or resulting in death. Secondary exploratory outcomes included wound complications defined as a deep surgical site infections (SSI) based on the Centers for Disease Control and Prevention criteria that required operation, and VTE (including massive, sub-massive, or clinically significant pulmonary embolism and clinically significant deep vein thrombosis (either distal or proximal)). No screening of asymptomatic patients for VTE events was done. All adverse events were reported to the IRB as per local requirements. Two medical monitors reviewed the safety of the trial and all serious adverse events.

Statistical Analysis

The study's sample size calculations were based on a retrospective review of the study centers database, which determined a 1-year historic bleeding complication rate of 15% in the study population. Based on arthroplasty literature, we hypothesized that aspirin would be associated with a 5% absolute reduction bleeding complications. Using a one-sided Fisher's Exact sample size calculation, an alpha of 0.05, and an allocation ratio of 1:1, a sample of 1150 patients would provide 80% power. This target sample was inflated to 1380 to allow for up to 20% loss to follow up. Within a year of starting the trial, funding was obtained to commence a large pragmatic trial comparing these two interventions with a primary endpoint of pulmonary embolism-related death. This trial was subsequently stopped after the enrollment of 329 participants, for which the safety of these two interventions was assessed

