Analysis followed the intention-to-treat principle and included all patients in the groups to which they were randomly assigned. Bivariable analysis and multivariable logistic regression model were used to assess the association between type of VTE prophylaxis and the primary and secondary endpoints. The treatment effects were reported as odds ratios (OR) and 95% confidence intervals (CI). The analyses adjust for the time each patient is at risk of the analyzed study event, to a maximum of 90 days. Patients who did not complete the 90-day follow up were deemed at risk from their time of enrollment until their last documented follow-up. Kaplan-Meier curves were used to plot the time to study events by treatment arm.

Patient crossover and contamination was assessed at several thresholds including $\geq 5\%$, $\geq 10\%$, $\geq 25\%$, $\geq 50\%$ of the patient's total study doses being the non-allocated prophylaxis medication. All thresholds were assessed in a secondary as-treated analysis. A threshold of more than 50% of the patient's total study doses being the non-allocated prophylaxis medication is presented for the as-treated analysis in the results. Factors associated with patient crossover in this study sample were also assessed.

At the completion of the trial, we investigated possible effect measure modification by patient smoking status, history of VTE, mechanism of injury (high energy versus low energy), fracture location (upper extremity versus lower extremity), fracture severity (open fracture versus closed fracture), and non-orthopaedic injury (abdomen, head, or chest) determined by an Abbreviated Injury Scale score of ≥ 2 . Each variable was added into the primary analysis as an interaction term. Statistically significant interactions were then analyzed stratifying by the effect measure modifier. The treatment effects in the stratified analysis were reported as odds ratios (OR) and 95% confidence intervals (CI), adjusting for time at risk.

All analyses were performed using JMP Pro Version 13 (SAS Institute, Cary, NC). This study was registered with ClinicalTrials.gov (NCT02774265).

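### The as-treated analysis labels patients by their share of all study doses, including doses after the event, so a bleed followed by a switch can be charged to the drug started afterwards

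*Combined protocol and SAP*

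**What the plan says.** The Statistical Analysis section makes intention-to-treat the main analysis. It then defines crossover by the proportion of a patient's study doses that were the other drug, lists cut-offs of at least 5%, 10%, 25% and 50%, and adds: "All thresholds were assessed in a secondary as-treated analysis". On what is reported, it says: "A threshold of more than 50% of the patient's total study doses being the non-allocated prophylaxis medication is presented for the as-treated analysis".

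Three other statements bear on the point:

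- On follow-up: "The analyses adjust for the time each patient is at risk of the analyzed study event, to a maximum of 90 days".
- On crossover, under Intervention and Procedures: "Any contamination or unplanned crossover was closely monitored".
- On its causes, under Statistical Analysis: "Factors associated with patient crossover in this study sample were also assessed". The factors are not listed.

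No section limits the dose count to doses before the event, makes exposure time-varying, or assigns an event to the drug being taken when it happened.

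**The concern.** The exposure label is fixed by what happens over the whole course, but the outcome may occur early in it. If a bleed prompts a change of drug, the outcome determines the exposure. The bleed leaves the group of the drug on which it occurred and enters the group of the drug chosen in response. This is reverse causation built into the definition.

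The design leaves that route open. On masking: "Surgeons and patients were not masked to the treatment groups". On the length of the course: "The duration of prophylaxis was at the treating surgeon's discretion, with no minimum or maximum duration". A surgeon can see which drug the patient was on, change it, and continue treatment long enough for the second drug to supply most of the doses.

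The as-treated result could then show a drug difference that does not exist or hide one that does. Under no drug effect this needs two things: switching that follows bleeding, and a different frequency of such switching in the two arms. Stopping prophylaxis after a bleed relabels nobody.

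**Working it through.** **The plan's own figure.** This point disputes no stated number. As a baseline check, the one-sided Fisher's exact test at 5% with 575 per arm and 15% versus 10% has power 0.8003, so the target of 1150 for 80% power reproduces.

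**Inputs from the Statistical Analysis section.** 329 enrolled, 1:1 allocation, 15% historic bleeding over 1 year, and a hypothesised 5-point reduction with aspirin. Assumption: the 15% applies to 90 days. Then N = 329/2 = 164.5 per arm, and expected bleeds are B = 164.5 × 0.15 = 24.7.

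**Step 1: effect of each relabelled patient.** Let k be the net number of bleeders moved from LMWH to aspirin. The numbers without a bleed do not change. With arm risks r_A and r_L,

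OR (aspirin vs LMWH) = [(N·r_A + k) / N(1 − r_A)] ÷ [(N·r_L − k) / N(1 − r_L)].

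With equal risks this reduces to (B + k)/(B − k). For k = 1: 25.675/23.675 = 1.08.

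| k | OR, no drug effect | OR, true 15% vs 10% |
|---|---|---|
| 0 | 1.00 | 0.63 |
| 1 | 1.08 | 0.70 |
| 2 | 1.18 | 0.77 |
| 3 | 1.28 | 0.85 |
| 4 | 1.39 (95% CI 0.75–2.56) | 0.93 |

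**Step 2: how many patients might move.** Let d be the difference between arms in the fraction of bleeders who switch. Let q be the chance that the course is longer than twice the switch day, which is what the more-than-50% rule requires. Then k = d·q·B, the bleeding rate cancels, and with no drug effect OR = (1 + dq)/(1 − dq).

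The documents give neither d nor q. For illustration, assume a mean bleed day of 5 or 10, a switch 1 day later, and exponential, gamma (shape 4) or fixed course lengths:

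| Mean course | q | (a) 20% of LMWH bleeders switch, 0% of aspirin | (b) 20% vs 10% | (a) if 15% vs 10% is true |
|---|---|---|---|---|
| 30 days | 0.56–0.94 | 1.25–1.46 | 1.12–1.21 | 0.83–0.99 |
| 14 days | 0.36–0.70 | 1.15–1.32 | 1.07–1.15 | 0.75–0.89 |
| 7 days | 0.19–0.39 | 1.08–1.17 | 1.04–1.08 | 0.69–0.76 |

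Example: d = 0.20 and q = 0.94 give 1.188/0.812 = 1.46. Case (a) relabels about 3–5, 2–3 and 1–2 of the 329 patients for the three course lengths. Simulated false-positive rates are 10–22%, 7–15% and 5–9%, against about 5% with no switching. In case (b) they are 6–9%, 5–7% and 4–6%. If only aspirin bleeders switch (20%), the OR is 0.68–0.93. Equal switching, or switching unrelated to bleeding, gives no material bias when there is no drug effect.

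**Step 3: does anything in the plan repair this?**

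- The endpoint model is described thus: "Bivariable analysis and multivariable logistic regression model were used to assess the association between type of VTE prophylaxis and the primary and secondary endpoints". Adjusting it for time at risk changes the follow-up credited to a patient, not the drug label. With follow-up time as a linear or log covariate, the simulated OR changes by about 0.001 or less.
- Agreement across thresholds is no reassurance. Anyone above 50% is also above 5%, 10% and 25%, so the lower cut-offs relabel the same patients and more. Case (a) over all course lengths gives 1.15–1.50 (≥5%), 1.14–1.50 (≥10%), 1.12–1.49 (≥25%) and 1.08–1.46 (>50%).
- Monitoring crossover and assessing its factors do not change the label, and a prior event is not named as a factor.

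**Step 4: candidate remedies.**

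- Majority of pre-event doses: with no drug effect and 20% switching from LMWH to aspirin unrelated to bleeding, the OR is 0.85–0.95, where the existing total-dose rule gives 0.99–1.01. Patients must stay event-free long enough to accumulate a majority on the second drug, which is immortal time.
- Exposure updated by day, stratified by day: the rate ratio in cases (a) and (b) is 0.98–1.02 with exact or latest-possible switch dates, and 0.64–0.66 with exact dates if 15% versus 10% is true. A person-day logistic model with exact dates gives 0.98–1.01 under no drug effect.
- Earliest-possible switch dates keep part of the bias: 1.02–1.23 in (a) and 1.00–1.10 in (b), assuming a mean 6-day admission and contacts on days 14, 42 and 90.

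**The case against.** The strongest reply is that this is a secondary analysis, that intention-to-treat is untouched, and that no switching after a bleed is documented. The endpoint includes hemoglobin drops and transfusions, and nothing says these lead to a change of drug. Bleeds may also come later than days 5 to 10. With a mean bleed day of 20 or 30, case (a) falls to about 1.03–1.23 and case (b) to 1.02–1.11. An interval of 0.75–2.56 shows that sampling error exceeds the shift, and the proposed model is post hoc and depends on approximate outpatient dates.

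Much of this stands. The bias is conditional, the illustrated ranges are not bounds, and the trial's main result is not at risk. But the labelling rule is stated rather than merely left open, and the plan chooses to present its result. Imprecision does not excuse a systematic shift. Unknown size is a reason to report the count that would settle it; if nobody over the threshold switched after an event, the concern about the presented result is closed.

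The objection is also right that the 50% wording is minor. The cut-offs are introduced as examples, so listing at least 50% and presenting more than 50% is an inconsistency to tidy, not a contradiction.

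**Conclusion.** The concern holds, for the secondary as-treated analysis only. On a plain reading the rule counts doses given after the event, and nothing else in the plan corrects for that. About 25 bleeds are expected per arm, so one to four net relabelled patients move a null OR to 1.08–1.39, and four nearly erase the hypothesised effect (0.63 to 0.93). These figures rest on 15% over 90 days and near-equal arms. The number actually relabelled, and the direction, cannot be known from the documents; the effect runs from negligible to material. The change should be made, but it does not threaten the main conclusion. Confidence is medium.

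**What to change.** 1. Keep the threshold analyses, describe them as open to reverse causation, and report by arm how many patients over each threshold switched after their event.
2. For each endpoint, add one secondary as-treated analysis with exposure updated daily from enrollment to the first event, last documented follow-up or day 90, charging each event to the drug in use at that time. A time-varying Cox or day-stratified rate model would serve; a person-day logistic model stratified by day stays closer to the plan. State how days after the last dose are labelled.
3. Do not substitute the majority of pre-event doses.
4. Add a prior study event to the crossover factors assessed.
5. Use either at least 50% or more than 50% throughout.

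The cost is one secondary analysis, one count table and some SAP wording, plus a check that the named software fits the model. The analysis would be post hoc, would give a hazard, rate or per-day odds ratio instead of the plan's OR, and would still be confounded by who switches. Doses were recorded daily only during the index admission, so outpatient switch dates need an earliest/latest-date sensitivity analysis. Because earliest-date coding retains some bias, use the chart's order of bleed and switch wherever it is recorded.

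### The secondary as-treated analysis names no adjustment beyond time at risk, so its odds ratio is confounded if prognosis affects switching differently in the two arms

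*Combined protocol and SAP*

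**What the plan says.** All of this is in the Statistical Analysis section unless noted.

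- The main analysis is by intention to treat. The model is described as multivariable logistic regression, without a covariate list.
- The one adjustment named is for follow-up: "The analyses adjust for the time each patient is at risk of the analyzed study event, to a maximum of 90 days".
- Crossover is measured as the share of a patient's total study doses that were the non-allocated drug. Several cut-offs feed a secondary as-treated analysis, and the version reported uses more than half.
- On who crossed over, the plan says only: "Factors associated with patient crossover in this study sample were also assessed".
- Smoking, history of VTE, mechanism of injury, fracture location, open versus closed fracture, and non-orthopaedic injury (AIS score of 2 or more) are listed as possible effect modifiers of the primary analysis. They are not mentioned for the as-treated analysis.
- Under Randomization and masking: "Surgeons and patients were not masked to the treatment groups".

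**The concern.** Once patients are grouped by drug received, randomization no longer balances the groups. With open-label care, switching can depend on how ill a patient is. The primary endpoint includes a hemoglobin drop of 2 g/dL or more and transfusion, both of which severe injury can plausibly produce on either drug. If sicker patients leave one arm more readily than the other, they accumulate in one as-treated group and raise its bleeding rate. Time at risk corrects for length of follow-up; it does not make switchers comparable with non-switchers.

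There is a second route to bias. Because the dose share covers all study doses, a drug change made after a bleed, and because of it, can move the patient into the other as-treated group. The outcome then determines the exposure.

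The as-treated result is meant to be presented. The trial stopped at 329 patients against a target of 1380, so the intention-to-treat estimate is imprecise and readers may lean on supporting analyses.

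**Working it through.** **Plan's own figure.** The documents give no figure for crossover or as-treated bias. Their one relevant calculation is the sample size: a control rate of 15% ("determined a 1-year historic bleeding complication rate of 15% in the study population"), a 5-point reduction, one-sided Fisher's exact test at 0.05. Exact power at 575 per arm is 80.03%, so 1150 reproduces. It serves here only as the source of the 15% event rate, which is a 1-year historic figure applied to a 90-day endpoint.

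**Assumptions (none from the documents).** Equal arms; no drug effect; 25% of patients severe, bleeding at 30%, and the rest at 10%. Overall: 0.25 × 0.30 + 0.75 × 0.10 = 15%.

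**Formula.** Let aS and aM be the shares of severe and other aspirin patients who switch to LMWH, and lS and lM the shares of LMWH patients who switch to aspirin. Relative to an arm size of 1, the as-treated LMWH group has

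- severe: 0.25 × (1 − lS + aS)
- other: 0.75 × (1 − lM + aM)

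and the aspirin group is the mirror image. Each group's bleeding rate is 10% + 20% × its severe share.

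**Worked case** (aS 25%, aM 5%, lS 5%, lM 15%).

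- LMWH: severe 0.25 × 1.20 = 0.300; other 0.75 × 0.90 = 0.675; severe share 0.300/0.975 = 30.8%; rate 16.15%.
- Aspirin: severe 0.25 × 0.80 = 0.200; other 0.75 × 1.10 = 0.825; severe share 0.200/1.025 = 19.5%; rate 13.90%.
- OR = (0.1615/0.8385)/(0.1390/0.8610) = 1.19, a spurious difference of 2.25 points.

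**Range.**

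| Selection | aS/aM | lS/lM | OR, LMWH vs aspirin |
|---|---|---|---|
| Opposite in the two arms, milder | 15/5% | 5/10% | 1.09 |
| Opposite, worked case | 25/5% | 5/15% | 1.19 |
| Opposite, stronger | 40/5% | 5/25% | 1.38 |
| From aspirin only, milder | 15/5% | 5/5% | 1.06 |
| From aspirin only | 25/5% | 5/5% | 1.13 |
| Equal in both arms | 25/5% | 25/5% | 1.00 |
| From LMWH only, milder | 5/5% | 15/5% | 0.94 |
| From LMWH only | 5/5% | 25/5% | 0.89 |
| From LMWH only, stronger | 5/5% | 40/5% | 0.81 |

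**Simulation.** 2000 trials of 329 patients, no drug effect, 15% overall bleeding, 30% sicker patients, 5% background switching, extra switching from aspirin to LMWH among the sicker. Odds ratios are LMWH vs aspirin; rejection is at two-sided 5%.

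| Risk ratio in sicker | Sicker aspirin patients switching | As-treated OR | Rejection | OR with severity in model | Rejection |
|---|---|---|---|---|---|
| 2 | 20% | 1.06 | 5.3% | 1.01 | 5.4% |
| 2 | 40% | 1.15 | 7.0% | 1.00 | 5.1% |
| 3 | 20% | 1.11 | 5.6% | 1.01 | 4.7% |
| 3 | 40% | 1.25 | 10.5% | 1.00 | 5.0% |

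The intention-to-treat OR stayed between 0.99 and 1.01. Here the model contains the true severity variable, so removal of the bias is a best case; measured proxies would remove part of it. Switching after a bleed was not simulated.

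**Scale against sampling error.** With 329 patients and 15% events, SE(log OR) ≈ √(4/(329 × 0.15 × 0.85)) = 0.31, so a 95% interval spans a factor of about 1.83 either way. The worked-case bias is ln(1.19)/0.31 ≈ 0.57 SE; the strongest case is about 1.05 SE.

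**The case against.** The strongest reply is that adjustment is unspecified, not shown to be absent. The word multivariable leaves room for covariates the text does not name. That stands: the actual model cannot be checked from the documents. But if covariates were used, they need listing; if not, the contrast is uncontrolled. Either way the plan as written does not protect this comparison.

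Second, the analysis is secondary and the main one is by intention to treat. That stands too, and it limits the weight of the point.

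Third, the size depends on the direction assumed. This also stands: with equal selection in both arms the bias is zero, and with selection from LMWH only it reverses.

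A reader might infer more than the text supports:

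- That the plan has found what drives crossover, and that severity is among the drivers. It reports no factors and no results.
- That both directions of crossover were pooled, so opposing factors could cancel. The text does not say whether the assessment was overall or by arm.
- That surgeons chose who switched, and moved high-risk patients to LMWH. The documents state only that surgeons and patients were unmasked. Patient preference and adherence are equally compatible.
- That the bias is large against the design effect (15% vs 10%, OR (0.15/0.85)/(0.10/0.90) = 1.59). That effect belonged to a 1150-patient design; at 329 patients the plausible bias is about one standard error or less.

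**Conclusion.** The concern holds for the secondary as-treated analysis only. The plan regroups patients by majority drug received in an open-label trial, names time at risk as the sole adjustment, and does not connect the crossover factors or the baseline injury variables to that model. The resulting odds ratio is confounded if prognosis affects switching differently by arm.

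Under the assumed rates, with no drug effect, it lies at about 1.06 to 1.38 (LMWH vs aspirin) when sicker aspirin patients move to LMWH. With selection from LMWH only it is about 0.89 at 25% versus 5% switching, nearer 1 with milder selection and lower with stronger. With equal selection it is 1.00. Neither the presence of bias nor its direction can be established from the documents, so it would be wrong to read the as-treated result as known to favor aspirin. The intention-to-treat conclusion is not touched. The change is worth making because the variables are already collected and time at risk alone does not address the problem.

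**What to change.** 1. In the as-treated model, or through inverse-probability weights for drug received, adjust for mechanism of injury, open fracture, fracture location, non-orthopaedic injury (AIS score of 2 or more) and history of VTE, all as they stood before randomization, in addition to time at risk. Name them in the plan.
2. Assess crossover factors separately by allocated arm.
3. Classify exposure from doses up to the event only. Baseline adjustment does not repair reclassification after a bleed.
4. Label the result as a non-randomized comparison.

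**Cost.** A short reanalysis of data already held, and a somewhat wider interval. At 15% of 329, about 49 events are expected; five covariates plus drug and time make seven parameters, about seven events each. A weighted, penalized or more parsimonious model may be needed. Step 3 needs dated doses: these were monitored daily during the index admission, but outpatient adherence was assessed at clinic visits, so timing after discharge may be approximate.

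An instrumental-variable (complier) estimate is optional. It rests on exclusion and monotonicity assumptions. Partial crossover strains them, since patients with up to half of their doses non-allocated still count as having received their assigned drug.
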